4.3 RISKS AND BENEFITS ANALYSIS

Expected but rarely occurring side effects related to microwave ablation include pain, fever, ascites, nausea, vomiting, general feeling of tiredness, bleeding, seeding, thrombosis, collateral organ injury, pneumothorax, pleural effusion, pneumonia and liver failure. In addition, it is expected but rare to see minimal collection of fluid or blood in the liver and heat damage to the adjacent areas from the CT scan and other imaging done after the procedure, and this can occur without any other sign and symptom. For pregnant patients, the potential risks to the patient and/ or baby have not been established.

4.3.1 Comparison with Other Microwave Ablation Systems:

Clinical Efficacy

The Certus 140 has the same intended use as other microwave ablation systems. The power levels of the Certus 140 provide clinicians with greater flexibility than many of the other systems currently available, including the ability to drive 3 probes, in-phase, at one time as well as having a higher top end power (140 W for a single probe) than most other systems. However, the total power available does not exceed other microwave systems on the market and thus does not introduce new risks. Multiple ablation probe types are available.

New Hazards or Intended Uses:

All hazards associated with the use of the Certus 140 have been identified and appropriately mitigated. Design considerations were taken to reduce the risks associated with existing microwave ablation systems, including improved system usability and cable management. The Certus 140 does use a CO₂ cooling system where all other microwave systems use sterile water, but the risks associated with this cooling system do not differ from the risks inherent in cryogenic ablation systems, also widely accepted in clinical use. Thus, the Certus 140 does not introduce new hazards or intended uses.

Clinical Benefit:

The Certus 140 2.45 GHz Ablation System is the same fundamental science and technology as other microwave ablation systems commercially available. As noted in the literature review above, microwave ablation has been generally accepted by the clinical community to be safe and effective and thus the Certus 140 can be considered safe and effective.

To date, over 25,000 patients in the US have had ablations performed using the Certus 140 system.

The Adverse Events associated with the Certus 140 System and Probes can be categorized as follows:

1. Mechanical probe breaks due to excessive force applied during probe placement, often through and around boney structures and/or cartilage.
2. Skin burns due to user placing probe improperly close to the patient's skin or delivering power for excess time and power given the probe placement.
3. Known risks associated with thermal ablation not associated with device failure or misuse.
4. Patient developed a bronchopleural fistula after a lung ablation procedure due to user error.

Regulatory Evidence of Substantial Equivalence

Additional information of the Certus 140 substantial equivalence may be found in the product's US FDA 510(k) clearance as below:

Product	FDA 510(k) Clearance
Certus 140 (including LK, LN and SR Ablation Probes	K100744
Certus 140 (including PR Ablation probes)	K113237
Certus 140 (SW Update to add Surgical SW)	K122217
Certus 140 (including CertuSurgGT Surgical Tool)	K130399
Ablation Confirmation SW Option	K160313
Certus 140 (including 15 ga probes)	K160936

4.3.2 Comparison with Radiofrequency Ablation Systems:

The subject assessments and procedure for microwave ablation (MWA) procedure being performed with the study devices are similar to the radiofrequency ablation (RFA) procedure that subjects would receive as part of their standard of care prior to the availability of MWA at the site.

To date, there is no reported difference in the reported adverse events between RFA and MWA.

In a meta-analysis by Huo et al⁴⁷, MWA and RFA had similar 1–5-year overall survival, disease-free survival, local recurrence rate, and adverse events. In terms of adverse events, MWA and RFA have similar low rates of complications, as identified in the same meta-analysis by Huo et al, and previous systematic reviews and multicenter trials^{18, 48} also found similar low rates of complications (4.1% for RFA and 4.6% for MWA).

4.3.3 Potential Benefit to Subjects:

The main benefits to Subjects from participation in this study are that they will be treated with a new microwave ablation technology, and the Sponsor will supply the study devices free of charge to the site who will treat the Subjects. There is no evidence that MWA is inferior to RFA but there is a strong suggestion that MWA is better for larger lesions^{12, 49}. As a result, subjects in the study may experience an improved result over standard of care treatment with RFA. The knowledge gained from this clinical trial may also help future microwave ablation patients.

5.0 SCIENTIFIC RATIONALE

5.1 STUDY RATIONALE

While there are several treatment options for hepatocellular carcinoma, there is a limitation to current options for microwave ablation in Korea. There has been no prospective clinical trial with the study device outside of United States.

The primary focus of this study is to assess the safety and effectiveness of NeuWave Medical's Certus 140™ 2.45 GHz Ablation System, Probes and Accessories in the ablation (coagulation) of the liver in percutaneous settings. Specific goals are to monitor the completion of ablation, specifically technical success immediately after ablation and technique success during the follow-up period of 36 months, local tumor progression rate and survival rate as well as adverse events in the Korean patient population.

The results from this study are expected to provide a review of the use of devices in microwave ablation of the liver. Data acquired in this study will provide safety and technical effectiveness data and user experience in a Korean patient population. This data, along with health economic information, will provide input for future innovations within the microwave ablation pipeline and potentially influence local clinical practice guidelines for the treatment of liver cancer.

5.2 STUDY DESIGN RATIONALE

The study is designed as a prospective, non-comparative, single center study with a cohort of 30 subjects. The follow-up period of up to 36 months was selected to cover the recovery period after ablation and the recommended intensive monitoring period for evaluation of progression-free survival and overall survival.

5.3 RATIONALE OF STUDY POPULATION

Subjects at an early stage of Hepatocellular Carcinoma (HCC), with tumor size of ≥ 2 cm and up to 5 cm at a single location and suitable for percutaneous microwave ablation are targeted for this study. The rationale for limiting the population to early stage of hepatocellular carcinoma and a single tumor within this larger size range is to address the gap in the evidence for effective treatment for this category of patients. For patients at an early stage of hepatocellular carcinoma and with tumor size ≤ 3 cm, curative treatment options could be resection, liver transplantation or ablation as per treatment guidelines. However, there is no clear evidence for effective treatment of larger than 3 cm lesions, and the efficacy of RFA in this category is not established. Hence, only 7 patients with HCC and tumor size > 3 cm were treated with RFA at the qualified study center in 2016. To ensure sufficient enrollment for this study, subjects with tumor size of ≥ 2 cm and up to 5 cm will also be included.

This study will provide clinical evidence of the use of microwave ablation in unresectable cases which still have relatively good liver function (Child Pugh Score of Class A or B) and slightly larger tumor size of ≥ 2 cm and up to 5 cm. The physician should consider using multiple probes for lesions ≥ 2 cm.

6.0 STUDY OBJECTIVE

To evaluate the outcomes of microwave ablation of Hepatocellular Carcinoma (HCC) of more than 2 cm and up to 5 cm.

6.1 PRIMARY OBJECTIVE

- Evaluate the technical success of microwave ablation of Hepatocellular Carcinoma (HCC) of ≥ 2 cm and up to 5 cm, using NeuWave Medical's Certus 140™ 2.45 GHz Ablation System and Accessories (study devices), immediately following the ablation procedure.

6.2 SECONDARY OBJECTIVES

- Evaluate the primary technique efficacy at 1 month after the ablation procedure.
- Evaluate local tumor progression (LTP)⁵⁰ rate at 1, 3, 6, 9, 12, 18, 24, 30 and 36 months after the ablation of the index tumor.
- Evaluate the primary efficacy rate⁵⁰.
- Evaluate the secondary efficacy rate⁵⁰.
- Evaluate the progression free survival and overall survival rates at 36 months after the ablation procedure.
- Evaluate safety through the type and frequency of adverse events through 3 months and cumulatively through study completion.
- Evaluate quality of life before the ablation procedure and at each post-ablation visit.
- Evaluate the health economics associated with the ablation procedure

7.0 STUDY DESIGN

7.1 OVERALL STUDY DESIGN AND PLAN - DESCRIPTION

This prospective, single-arm single center study will provide clinical data using the study devices. Individuals scheduled for microwave ablation of the liver in accordance with their institution's SOC, and who meet study entry criteria, will be screened for enrollment after providing informed consent. Subjects will be followed for up to 36 months following the ablation procedure for safety and outcomes. Prospective subjects will be informed about the nature of the research, given the Informed Consent Form (ICF) to read, and if the subject understands the consent, will be asked to provide written consent (the ICF).

Enrollment will continue until 30 eligible subjects complete the 3-month visit after ablation (Visit 4) for the primary effectiveness and safety analysis.

Additionally, in order to reduce the variability between investigators in assessing the CT images (and, as needed, MRI and Ultrasound) and to minimize potential bias, an independent radiologist reviewer from the participating site, and who is not an investigator, will conduct a review of all the CT scans taken from screening and throughout the clinical study. The assessment by the independent reviewer will only be used for the purpose of statistical analysis while the assessment by the investigators will be used for the treatment of the subjects in the study.

7.2 STUDY ENDPOINTS

Primary:

Technical Success, defined as complete tumor ablation with adequate or insufficient margin, based on contrast-enhanced MRI and CT scans immediately following the ablation procedure.

Secondary:

- Primary Technique Efficacy, defined as complete tumor ablation with adequate or insufficient ablation margin, based on contrast-enhanced MRI and CT scans follow-up at 1 month after the ablation procedure;
- Local tumor progression (LTP) rate, evaluated at 1, 3, 6, 9, 12, 18, 24, 30 and 36 months after the ablation of the index tumor;
- Primary efficacy rate, defined as the percentage of target tumors successfully eradicated following the ablation procedure;
- Secondary efficacy rate, defined as the percentage of tumors that have undergone successful repeat ablation following identification of local tumor progression;
- Progression free survival and overall survival rates at 36 months after the ablation procedure;
- Rate of adverse events reported through 3 months and cumulatively through study completion; Quality of Life, as measured by VAS pain score, EORTC QLQ-C30 and EORTC QLQ-HCC18, before the ablation procedure and at each post-ablation visit;
- Health economics associated with the ablation procedure: complete procedure time, ablation time, no. of ablations, length of stay, no. and types of probes used.

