12.1.1.11 Reporting Adverse Events

Investigator's Responsibility:

The Investigator is required to report all AEs experienced by the subject from Visit 2B until the subject completes Visit 4 (3 months after the ablation procedure) or withdraws before Visit 4. All AEs during this time period, regardless of their relatedness to the study device(s) or procedure, must be reported in the AE eCRF within 2 weeks after the site becomes aware of the information. The investigator will evaluate the severity of the event, and its relatedness to the study device or procedure. Any necessary medical management of the event will be recorded in the subject's medical record/source document. All AEs must be followed until resolution or until they become stable but ongoing.

Sponsor's Responsibility:

The Sponsor will follow MFDS's guideline to report safety events related to the study medical devices with the timeline which is regulated by law.

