12.1.1.12 Reporting Serious Adverse Events

Investigator's Responsibility:

The Investigator is required to complete the AE eCRF for:

- All SAEs experienced by the subject from Visit 2B until the subject completes Visit 4 (3 months after the ablation procedure) or withdraws before Visit 4
- All expected and unexpected serious adverse device effects experienced by the subject, all life-threatening events, event that results in death and all SAEs with definite, probable, possible, or unknown relationship to the study device or study procedure after Visit 4 until the subject completes Visit 11 or withdraws before Visit 11.

All serious adverse events must be reported to the Sponsor by the site within 24 hours after the site becomes aware of the information by entering the data into the AE eCRF. The Investigator must avoid disclosing the subject information, by using the ID code, instead of using name, or home address. In case of death, the Investigator has to report as much information as there is available to the Sponsor, including the death certificate and/ or autopsy report (only when autopsy is performed).

The Investigator must report all expected and unexpected serious adverse device effects, and all life threatening events and events resulting in death to the IRB within the timelines regulated by their IRB procedures.

Sponsor's Responsibility:

The Sponsor will follow MFDS's guideline to report safety events related to the study medical devices with the timeline which is regulated by law.

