15.8.6 Analysis of Safety

The number and percentage of subjects experiencing adverse events (AEs) will be summarized at the preferred term level using the SIR clinical practice guidelines for event categorization. Summarization of AEs will also be provided by (1) by relationship to study procedure (MWA); (2) by relationship to the device (study devices); and, (3) by maximum severity. Serious AEs will be summarized in a similar manner.

Concomitant procedures and hospital readmission will be summarized with counts and percentages. Summary statistics for laboratory parameters over time may be provided. Post ablation concomitant medications will be listed for all subjects.

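### The cumulative adverse event rate and the AE/SAE summaries mix two reporting rules: all events to Visit 4, then a restricted list to Visit 11

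*Combined protocol and SAP*

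**What the plan says.** **Endpoint and objective.** Section 7.2 (repeated in the synopsis) lists "Rate of adverse events reported through 3 months and cumulatively through study completion". Section 6.2 has the matching objective: "Evaluate safety through the type and frequency of adverse events through 3 months and cumulatively through study completion".

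**Analysis.** Section 15.8.6 states: "The number and percentage of subjects experiencing adverse events (AEs) will be summarized at the preferred term level". It adds splits by relationship to procedure, relationship to device, and maximum severity, and then: "Serious AEs will be summarized in a similar manner". It names no period and no event class. Section 15.8.4 limits the safety summary of the first analysis to 3 months and gives no safety scope for the second.

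**Collection to Visit 4.** Section 12.1.1.11: "The Investigator is required to report all AEs experienced by the subject from Visit 2B until the subject completes Visit 4". Section 12.1.1.12 has the same rule for SAEs. Note 8 to Table 1 ends this period at 3 months instead of at completion of Visit 4.

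**Collection after Visit 4.** Section 12.1.1.12 requires "All expected and unexpected serious adverse device effects experienced by the subject, all life-threatening events, event that results in death", together with SAEs whose relationship to device or procedure is definite, probable, possible or unknown, up to Visit 11. Note 8 has the same list. Sections 11.7 to 11.10 repeat it and say that only these events go to the sponsor after Visit 4.

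**Text that points the other way.** The Safety row of the synopsis promises recording and reporting of all AEs for the whole study. Section 12.1.1.2 defines an AE as occurring at any time from treatment to Visit 11. Sections 12.1.1.3 and 12.1.1.4 require adverse device effects, expected or not, to be reported and set no end date.

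**The concern.** The endpoint asks for a rate over the whole study, but the data for a complete rate stop at Visit 4. The final AE and SAE tables would look like three-year incidences, although for some classes of event they are Visit 4 incidences carried forward.

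Two kinds of table are affected. The overall and preferred-term percentages would miss certain late events. The splits would also be uneven: related SAEs accrue for about 36 months, while most SAEs judged unrelated stop accruing at Visit 4, so the two rows cannot be compared. The same applies to maximum severity, since a later and worse event off the list cannot raise a subject's maximum. Nothing in the tables as planned would tell the reader this.

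**Working it through.** The plan gives no AE rate to reproduce, so the check sets the collection rules against the analysis rule.

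**Step 1. Which classes are collected, and when.**

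| Class | To Visit 4 | Visit 4 to Visit 11 |
|---|---|---|
| Deaths and life-threatening events | yes | yes |
| Serious adverse device effects, including those that might have become serious (12.1.1.6) | yes | yes |
| SAEs of definite, probable, possible or unknown relationship | yes | yes |
| SAEs judged not related, neither fatal nor life-threatening | yes | not on the list |
| Non-serious AEs outside the serious device effect definition | yes | not on the list |

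The first three rows follow one rule throughout. The last two change rule at Visit 4. Within the last row, non-serious device effects are unclear, because 12.1.1.3 and 12.1.1.4 set no time limit while the list in sections 11 and 12.1.1.12 names only serious ones.

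**Step 2. Direction.** Let E be the subjects with an event up to Visit 4, L those with a late listed event, and U those with a late unlisted event. The complete count is the size of E ∪ L ∪ U; the count available is the size of E ∪ L. The denominator is the same (Safety Set, 15.6). E ∪ L is contained in E ∪ L ∪ U, so the available percentage cannot exceed the complete one. The two are equal only if every subject in U is already in E or L.

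**Step 3. Share of follow-up under each rule.** With Visit 4 at 3 months: 3/36 = 8.3% under the full rule and 33/36 = 91.7% under the restricted rule. Section 15.3 allows ±28 days, which is 28/30.4375 = 0.92 months. The full-rule share then runs from (3 − 0.92)/36 = 5.8% to (3 + 0.92)/36 = 10.9%. These are shares of time, not of events.

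**Step 4. Scale per subject.** If k subjects have a given term only as a late unlisted event, that term's percentage falls by 100k/N points. Enrolment runs until 30 subjects complete Visit 4, with earlier terminators replaced (8.5, 15.8.5), and the Safety Set counts every attempted ablation, so N should be at least 30. For k = 1: 1/30 = 3.3 points, or 1/40 = 2.5 points at an assumed N of 40. The documents give no basis for k.

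**Step 5. The two cut-offs.** Take 3 months as day 91. Visit 4 may then fall from day 91 − 28 = 63 to day 91 + 28 = 119. A non-serious AE after an early Visit 4 but before day 91 is reportable under note 8 and not under 12.1.1.11. One after day 91 but before a late Visit 4 is the reverse. The gap is at most 28 days either way per subject.

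**The case against.** The best reply is that restricted late collection is a legitimate and openly stated choice. The endpoint speaks of reported events and already separates 3 months from the cumulative figure, the first analysis is limited to 3 months, the study is descriptive, and section 15.1 foresees a detailed SAP. All of that stands: the rule is not hidden and full late collection is not required. It does not settle the point. Reading the endpoint as events reportable under section 12 gives the same mixed number without a label, the objective in 6.2 does not carry the word, and no text provided defines the cumulative rate.

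The reply also limits how far the point reaches. Four stronger readings are tempting, and the documents do not support them:

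- *Every late non-serious event is lost.* Section 12.1.1.6 brings in device effects that might have led to a serious outcome.
- *Late SAEs are widely lost.* Section 12.1.1.9 uses the possible category even for events unlikely to be associated, and unknown relationship is reportable too. Only those judged not related, and neither fatal nor life-threatening, drop out.
- *The literature comparison planned in 15.7 is spoiled.* The safety column in Tables 3 and 4 is major complications (a few entries pool minor ones). Under 12.1.1.10 these are defined largely by admission, longer stay, disability or death, so procedure-related ones are mostly SAEs and remain reportable. What may be missed is mainly late minor complications.
- *The missing time limit in 12.1.1.3 and 12.1.1.4 shows an intention to collect late non-serious device effects.* Those sections omit the qualifier that limits AE and SAE reporting to reportable events, but so do 12.1.1.6 and 12.1.1.7. The omission shows that the text needs reconciling, not which reading is meant.

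**Conclusion.** The point holds as a mismatch between the cumulative endpoint, the collection rule and the analysis section. Run as written, the final AE and SAE percentages combine two ascertainment rules, and their error can only be understatement. It falls on late non-serious AEs outside the serious device effect definition and on late SAEs judged not related that are neither fatal nor life-threatening. The related and not-related SAE rows cover different periods.

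The size is unknown. The 3.3 points per subject is 1/30 and says nothing about how many subjects are affected. A reader might infer from the 91.7% share of follow-up that most events are missed; that does not follow, because the documents give no late event rate. A reader might also infer that the related share of SAEs will be overstated; that follows only if omitted late SAEs occur.

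The all-AE 3-month rate is essentially unaffected, apart from the cut-off wording and any subject moved to reduced follow-up before Visit 4. Rates for the classes collected throughout follow one reporting rule. Contact is sparser, however, for subjects retreated after progression, who are seen every 6 months and possibly by phone (11.10). The change should be made: it needs little more than wording and affects a stated secondary endpoint.

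**What to change.** 1. In 7.2 and 15.8.6, report all-AE and all-SAE incidence, with the relationship and severity splits, only to one stated cut-off. Reconcile the 3 months in note 8 to Table 1 with completion of Visit 4 in 12.1.1.11.
2. For the period through study completion, report only the classes collected throughout: serious adverse device effects, life-threatening events, deaths, and SAEs of definite, probable, possible or unknown relationship. Put the reporting rule in the table title, and note that subjects on the reduced schedule are contacted every 6 months, possibly by phone.
3. Reconcile the synopsis Safety row, and the device effect reporting text in 12.1.1.3 and 12.1.1.4, with the post-Visit 4 list.

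Items 1 and 2 are wording only and need no new data. Item 3 is wording too, unless the sponsor decides that late non-serious device effects are to be reported. That would add some AE forms at one site, for subjects already evaluated for all AEs at each follow-up visit (11.7). The price is a narrower long-term safety statement. A footnote giving the reporting rule under a combined table would be the minimum, but it would leave the relationship and severity splits mixed.
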